6.1 DETERMINATION OF SAMPLE SIZE

In Part 1 of the study, the adaptive SAD part, the planned sample size of 8 active per cohort was chosen not only to allow adequate assessment of safety and tolerability but also to increase the precision of the estimates of mean PK and urinary parameters, [REDACTED]

Up to 80 HVs will be included in Part 1 of this study. Up to 8 cohorts of 10 HVs (8 on active and 2 on placebo per dose level) are planned but, based on the analysis of emerging PK and safety data, additional cohorts may be included or subsequent cohorts modified.

For Parts 22a and 2b of the study, the PoM in CHB infected patients, a sample size of no more than 80 patients with CHB has been chosen (6 patients [Part 2a] and 8 patients [Part 2b] per dose cohort). It is anticipated that this sample size will allow characterization of the PK/PD (viral dynamic response) relationship, as well as safety and tolerability, in patients with CHB.

For Part 2c, approximately 16 patients will be enrolled into the initial 2 cohorts (8 patients in each cohort). If utilized, approximately 8 patients will be enrolled to each of the Cohorts 11 and 12. The sample size supports the assessment of response rate of undetectable qHBsAg at Week 24 follow-up in Cohorts 10, 11, and 12.

A sample size of 8 ensures that the associated lower 90% confidence limit is above 10%, if the observed response rate is at least 38% (i.e. at least 3/8), assuming a binomial distribution. This sample size is also considered reasonable to support the safety and tolerability objectives of all cohorts, as well as to allow characterization of the qHBsAg profiles in Cohort 9. The cohorts may be expanded up to 30 subjects if warranted by emerging PD and/or safety data. A sample size of 30 ensures that the associated lower 90% confidence limit is above 20%, if the observed response rate is at least 37% (i.e. at least 11/30).

6.2 SUMMARIES OF CONDUCT OF STUDY

Enrollment, major protocol violations and discontinuations from the study will be summarized by treatment and dose level. The number of healthy volunteers or patients who were randomized, discontinued and completed the study will be summarized. Reasons for premature study withdrawal will be listed and summarized by treatment and dose level. Demographic and other baseline characteristics will be summarized with descriptive statistics.

6.3 ANALYSIS POPULATIONS

6.3.1 Safety Analysis Population

All study subjects who have received at least one dose of the study medication, whether prematurely withdrawn from the study or not, will be included in the safety analysis.

6.3.2 Pharmacokinetic Analysis Population

Study subjects will be excluded from the pharmacokinetic analysis population if they significantly violate the inclusion or exclusion criteria, deviate significantly from the protocol or if data are unavailable or incomplete which may influence the pharmacokinetic analysis. Excluded cases will be documented together with the reason for exclusion. All decisions on exclusions from the analysis will be made prior to database closure.

6.4 SUMMARIES OF TREATMENT GROUP COMPARABILITY

Descriptive statistics will be generated for demographics, including sex, self-reported race, ethnicity, age and for Part 2 only: baseline disease characteristics including: HBV history (duration of HBV disease, mode of infection, HBV genotype, previous HBV treatments and outcomes, occurrence of NUC resistance). Baseline viral dynamics: HBsAg, HBV DNA and HBeAg will also be summarized.

Data for study drug administration and concomitant medication will be listed. The number of subjects who were randomized, discontinued treatment period, completed treatment period, discontinued study and completed the study (including follow-up period) will be summarized.

6.5 SAFETY ANALYSES

All safety analyses will be based on the safety analysis population.

All study subjects who receive at least one dose of study drug will be included in the safety analysis. The safety data, including AEs, ISRs, reason for withdrawal from study, laboratory data, ECG, concomitant medications, vital signs and physical examination results will be listed and summarized descriptively. Marked abnormalities will be flagged for laboratory data.

As appropriate, listings, summary tables and graphs (study subject plot and/or mean plots) will be provided for safety and tolerability assessments.

6.5.1 Adverse Events

The original terms recorded on the eCRF by the Investigator for adverse events will be standardized by the Sponsor by assigning preferred terms. Adverse events will be summarized by mapped term and appropriate thesaurus level.

AEs will be described by individual listings and frequency tables broken down by body system.

6.5.2 Clinical Laboratory Test Results

All clinical laboratory data will be stored on the database in the units in which they were reported. Study subject listings and summary statistics at each assessment time will be presented using the International System of Units (SI units; *Système International d'Unités*). Laboratory data not reported in SI units will be converted to SI units before processing. Laboratory test values will be presented by listings and descriptive summary statistics.

6.5.2.1 Standard Reference Ranges and Transformation of Data

Roche standard reference ranges, rather than the reference ranges of the Investigator, will be used for all parameters. For most parameters, the measured laboratory test result will be assessed directly using the Roche standard reference range. Certain laboratory parameters will be transformed to Roche's standard reference ranges.

A transformation will be performed on certain laboratory tests that lack sufficiently common procedures and have a wide range of Investigator ranges, e.g., enzyme tests that include AST, ALT, and alkaline phosphatase and total bilirubin. Since the standard reference ranges for these parameters have a lower limit of zero, only the upper limits of the ranges will be used in transforming the data.

6.5.2.2 Definition of Laboratory Abnormalities

For all laboratory parameters included, there exists a Roche predefined standard reference range. Laboratory values falling outside this standard reference range will be labeled "H" for high or "L" for low in study subject listings of laboratory data.

In addition to the standard reference range, a marked reference range has been predefined by Roche for each laboratory parameter. The marked reference range is broader than the standard reference range. Values falling outside the marked reference range that also represent a defined change from baseline will be considered marked laboratory abnormalities (i.e., potentially clinically relevant). If a baseline value is not available for a study subject, the midpoint of the standard reference range will be used as the study subject baseline value for the purposes of determining marked laboratory abnormalities. Marked laboratory abnormalities will be labeled in the study subject listings as "HH" for very high or "LL" for very low.

6.5.3 Vital Signs

Vital signs data will be presented by individual listings. In addition, tabular summaries will be used, as appropriate.

6.5.4 ECG Data Analysis

ECG data will be as summary descriptive statistics for the actual values and changes from baseline will be tabulated by nominal time for HR, QRS duration, PR and QTcF. For multiple measurements taken at a nominal time-point, the average of these measurements will be used as the value at that nominal time-point in all summaries. In addition, QTcF will be categorized at each time-point as ≤ 450 msec, $> 450-480$ msec, $> 480-500$ msec and > 500 msec and summarized. Similarly, a summary will be provided of the QTcF changes from baseline at each time-point categorized as < 30 msec, $30-60$ msec, and > 60 msec. Changes of the overall ECG interpretation, T-wave and U-wave morphology will be summarized.

6.5.5 Concomitant Medications

The original terms recorded on the study subjects' eCRF by the Investigator for concomitant medications will be standardized by the Sponsor by assigning preferred terms.

Concomitant medications will be presented in summary tables and listings.

6.6 PHARMACODYNAMIC ANALYSES

Pharmacodynamic parameters will be presented by listings and descriptive summary statistics separately by Part and/or cohorts.

6.6.1 Viral Dynamic Response Analyses

Summary descriptive statistics will be used to summarize the viral dynamic response outcome measure of quantitative HBsAg (log₁₀), actual and change from baseline in quantitative HBsAg at each time-point by dose group. Rate of decrease in quantitative HBsAg will also be summarized using descriptive statistics.

Plots of quantitative HBsAg (actual and change from baseline) over time will be utilized to compare the longitudinal profiles across doses.

Mean (SD) of HBsAg (actual and change) will be calculated for each dose level and plotted on one plot, different line types and symbols used to differentiate the dose levels. In addition, individual patient data will be plotted over time, one plot for each dose level.

Further exploration may include plots of quantitative HBsAg over time, grouped by baseline characteristics and/or demographics of interest.

All other exploratory viral dynamic responses will be listed by time-points as a minimum.

Further exploration of these exploratory responses for potential treatment effects may include longitudinal graphs and/or summaries.

6.6.2 PK/Viral Dynamic Response Analyses

The relationship between RO7062931 and dose, and metabolite(s) and dose if applicable, and the change of HBsAg at each time-point and rate of decrease will be explored by graphical analysis. The relationship between RO7062931 PK and urinary parameters and HBsAg will also be explored by graphical analysis. Assuming a monotonic relationship between HBsAg decrease and dose/plasma RO7062931, an appropriate exposure/dose-response model may be fitted to the data from Part 2a. This model may be used to guide dose selection for Part 2b, *and will be further developed with data from Parts 2b and 2c.*

6.6.3 Efficacy Analyses

The proportion of patients with undetectable qHBsAg and associated 95% binomial confidence intervals will be calculated at 24 week after the end of treatment. Patients with missing HBsAg measures at 24 weeks visit after the end of treatment and thereafter will be treated as non-responders.

6.7 PHARMACOKINETIC ANALYSES

Non-compartmental analysis using WinNonlin software will be used to calculate PK parameters where appropriate. Summary descriptive statistics of plasma PK parameters including C_{max} , T_{max} , AUC_{inf} , AUC_{last} , and $t_{1/2}$ for RO7062931 and any metabolites when available will be presented by cohort/treatment arm including mean, standard deviation (SD), coefficient of variation (CV), medians and ranges. Note: the geometric *or arithmetic* mean and associated CV% will be used to describe C_{max} , AUC_{inf} , AUC_{last} and $t_{1/2}$. Median values will be used to describe T_{max} . Where appropriate, data may be pooled and analyzed, for example, all single dose data may be pooled. Listings, summary tables and graphs (individual plots and/or mean plots) by treatment group will be provided. Descriptive statistics of urine PK parameters for RO7062931 and any metabolites will be presented, where available. PK and PD data from this study may be used to develop a population PK/PD model.

Where appropriate, listings and summary tables of nucleoside/nucleotide-analogues, tenofovir, tenofovir, alafenamide, entecavir, adefovir, or telbivudine concentrations will be provided based on the sparse sampling throughout the study.

6.8 EXPLORATORY ANALYSES

6.8.1 Liver and Kidney Biomarker Data

The exploratory safety parameters (see Section 4.6.1.5.6), will be explored graphically. Plots will include longitudinal plots for both actual result and change from baseline. Longitudinal plots will include individual subject responses by dose, as well as mean/median plots. Box and whisker plots may also be used to detect outliers.

6.9 INFLAMMATORY MARKERS, AUTOANTIBODIES AND ADA DATA

At minimum, any data that is collected as detailed in Section 4.6.1.5.3, and is available at the time of database closure will be listed and summarized using descriptive statistics. Data may also be explored graphically.

6.10 ANALYSIS TO SUPPORT DOSE-SELECTION

Bayesian adaptive methodology will be explored to help guide selection of doses and dosing regimen to be studied in Part 1 and Part 2b of this study. This methodology is exploratory and considered as supporting information only. Clinical judgment will always take precedence in making the final decisions.

6.10.1.1 Part 1

[REDACTED]

[REDACTED]

[REDACTED]

[REDACTED]

[REDACTED]

[REDACTED]

[REDACTED]

[REDACTED]

[REDACTED]

[REDACTED]

[REDACTED]

The aim of such a dual endpoint approach would be to estimate an optimal dose level which represents an optimal trade-off between safety and biomarker response.

[REDACTED]

6.10.1.2 Part 2b Dose Selection: First Two Cohorts

A repeated measures dose-response model will be fitted to the data observed in Part 2a to model the relationship between quantitative HBsAg decline over time. The dose selected to be studied in different dosing regimens in the first two cohorts of Part 2b will be the lowest dose that yields the greatest decline at any time-point. Furthermore, a dual endpoint methodology described above for Part 1, modeling the quantitative HBsAg decline simultaneously with DLE in order to select a dose that maximizes the PD effect (HBsAg decline) whilst controlling on safety (DLE) will also be explored.

The shape of the dose-response observed in Part 2a would determine the function that would be used to parameterize the HBsAg decline. The PD data and the safety data from Part 2a would be used to specify the priors.

6.10.1.3 Part 2b Dose/ Regimen Selection: Exploratory Cohorts

A response-adaptive approach will be explored to help guide the selection of the doses to be studied in the exploratory part of Part 2b using optimization criteria. Criterion that optimizes the dose-response parameters (D-optimality) as well as criterion that optimizes the target dose (TD-optimality) will be explored.

The HBsAg decline at Day 29 will be modelled against cumulative dose using the most appropriate dose-response model. These parameter estimates would then be used as initial parameters for model selection. The efficiency of a set of models, where the doses and dose regimens to be further explored in the exploratory part of Part 2b are varied, will be compared using the R function (optDesign) within the (dose-finding) package ([Bornkamp et al 2016](#)).

6.11 INTERIM ANALYSES

No interim analysis is planned for Part 1s 2a, and 2b of this study.

In Part 2c, administrative interim analyses will be conducted at Weeks 12 and 24 for the initial 8 enrolled in both Cohorts 9 and 10. Given the hypothesis-generating nature of this study, the Sponsor may choose to conduct additional administrative interim PD analyses. The decision to conduct additional interim analyses and the timing of the analyses will be documented in the Sponsor's trial master file prior to the conduct of the interim analysis. The interim analysis will be performed and interpreted by Sponsor study team personnel.

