All doses in Part 2 will be lower than, or equal to, the doses studied and considered to be well-tolerated in Part 1. Subsequent doses and regimens for Part 2b/2c will be selected on the basis of the analysis of Part 2a data. Part 2b will be initiated once Part 2a data have been analyzed. *The* total dose will not exceed 400 mg per day.

Due to the adaptive nature of this study, the actual number of dose levels and the number of study subjects/cohorts at each dose may be modified depending on emerging data. Planned doses may be adjusted (increased, decreased, or repeated) or dosing may be discontinued. After safety and PK data review (see Section [3.1.4](#)), study subjects may be requested to return to the site for additional safety or PK assessments, upon agreement between subjects, Investigators and the Sponsor.

3.1.1.3 *Part 2c: Extended Duration of RO7062931 Therapy in CHB Infected Patients*

Part 2c is an adaptive, open-label, non-controlled, multi-arm, multi-center, study to evaluate the efficacy and safety of RO7062931 following subcutaneous administration on top of SoC therapies (a NUC with/without PEG-IFN) in NUC-suppressed or treatment-naïve CHB patients ([Figure 2](#)). Both HBeAg positive and negative patients will be enrolled.

- *Cohort 9 will enroll NUC-suppressed CHB patients. Patients will receive RO7062931 on top of a NUC for up to 24 weeks. RO7062931 will be administered at a dose determined from study Parts 2a and 2b.*
- *Cohort 10 will enroll NUC-suppressed CHB patients. Patients will receive RO7062931 on top of a NUC plus PEG-IFN for up to 48 weeks. RO7062931 will be administered at a dose determined from study Parts 2a and 2b.*
- *Cohort 11 and 12 (optional cohorts) may enroll treatment-naïve immune-active CHB patients and/or different treatment combinations or treatment duration.*

All cohorts will initially enroll approximately 8 CHB patients per cohort. Initially the enrollment will occur sequentially (Cohort 9 will be followed by Cohort 10, see Section 4.3). At the end of treatment (either 24 or 48 weeks depending on cohort), all study treatment (RO7062931 and PEG-IFN) will be discontinued and all patients will be followed up for at least 24 weeks post-treatment follow up.

Based on emerging and accumulated PK, PD, efficacy and safety data from this study or other related studies, the initial cohorts may be expanded to enroll a total of 30 CHB patients. Enrollment of the expanded cohorts may be either sequential or parallel.

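### Part 2c cohorts may be expanded on emerging PD and efficacy data, but the planned pooled response rate takes no account of that selection

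*Combined protocol and SAP*

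**What the plan says.** - Section 3.1.1.3 sets the starting size: "All cohorts will initially enroll approximately 8 CHB patients per cohort". It then allows growth to a total of 30: "Based on emerging and accumulated PK, PD, efficacy and safety data from this study or other related studies, the initial cohorts may be expanded".
- Section 6.1 names a narrower basis: "The cohorts may be expanded up to 30 subjects if warranted by emerging PD and/or safety data". Section 3.1.2 names safety, tolerability, PK and PD. None of the three gives a threshold.
- Section 6.1 supports the sizes with precision statements: "A sample size of 8 ensures that the associated lower 90% confidence limit is above 10"% at 3/8 or better, and "A sample size of 30 ensures that the associated lower 90% confidence limit is above 20"% at 11/30 or better. It ties the response rate to Cohorts 10, 11 and 12.
- Section 6.11 plans the looks: "administrative interim analyses will be conducted at Weeks 12 and 24" in the initial 8 of Cohorts 9 and 10. The Sponsor may add further PD looks, and the study team performs and interprets them. The section does not say what the looks are for.
- Section 6.6.3 gives the final analysis: "The proportion of patients with undetectable qHBsAg and associated 95% binomial confidence intervals will be calculated" at 24 weeks after the end of treatment. It has no stage-wise or adjusted estimate.

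**The concern.** The PD measure in Part 2c is qHBsAg, and the response endpoint is undetectable qHBsAg. The data that may trigger expansion and the data that are finally summarised are therefore readings of one biomarker in the same first 8 patients. Pooling those 8 with the added patients is not stated outright, but it is implied by the total of 30 and by the 11/30 illustration. If a cohort goes on because its first 8 did well, those 8 carry a favourable chance component into the pooled estimate, and nothing planned would show it.

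The stake is the estimate itself. Part 2c is open-label with no concurrent control, so the response rate and its interval are its main efficacy result, and no comparison arm would reveal an inflated rate.

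**Working it through.** **Inputs.** First stage 8, total 30, so 22 added (3.1.1.3, 6.1). Counts of 3/8 and 11/30 with 90% limits (6.1). 95% interval in the analysis (6.6.3). *Assumptions, not in the documents:* a true rate of 20%, an expansion rule, 30 per cohort, and added patients from the same population.

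**1. The plan's own figures.** The exact lower limit L solves P(X ≥ x | n, L) = 0.05 for a two-sided 90% interval.
- 3/8: L = 11.1% (2/8: 4.6%).
- 11/30: L = 22.1% (10/30: 19.3%).

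Both statements reproduce, and each count is the smallest that qualifies. With the 95% interval of 6.6.3 the limits are 8.5% and 19.9%, and 12/30 (22.7%) is then the smallest count above 20%.

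**2. No selection.** With 30 fixed and a true rate of 20%, the mean estimate is 20% and P(X ≥ 11) = 2.56%.

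**3. Expansion on the endpoint itself.** Expand if at least k of the first 8 respond. The mean pooled estimate given expansion is (E[X1 | X1 ≥ k] + 22p)/30. For k = 3, P(X1 ≥ 3) = 20.3% and E[X1 | X1 ≥ 3] = 3.335, so (3.335 + 4.4)/30 = 25.8%.

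| k | P(expand) | Mean pooled rate given expansion | Bias (points) | P(≥11/30) given expansion | P(expand and ≥11/30) |
|---|---|---|---|---|---|
| 1 | 83.2% | 21.1% | +1.1 | 3.1% | 2.53% |
| 2 | 49.7% | 23.2% | +3.2 | 4.7% | 2.33% |
| 3 | 20.3% | 25.8% | +5.8 | 8.6% | 1.74% |
| 4 | 5.6% | 28.7% | +8.7 | 16.2% | 0.91% |

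With k = 3 the bias is +7.8 points at a true rate of 10% and +4.0 points at 30%.

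**4. Expansion on an imperfect on-treatment marker.** This is closer to what the Week 12 and 24 looks can show. Two simulated models, true rate 20%:
- Binary marker, sensitivity 0.7 to 0.9 and false-positive rate 0.2 to 0.4, expand on at least 3 or 4 of 8 positive: mean pooled rate 20.3% to 22.9%; P(≥11/30) given expansion 2.9% to 5.4%.
- Continuous marker correlated 0.5 to 0.8 with the latent response, best 20% to 50% of cohorts expanded: mean 21.1% to 23.2%; P(≥11/30) given expansion 3.4% to 5.9%.

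The bias is therefore about +0.3 to +3 points. The standard error of a rate of 20% in 30 patients is √(0.2 × 0.8/30) = 7.3 points.

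**5. Added patients alone.** Their expected rate is 20% whatever the rule. The standard error rises to √(0.2 × 0.8/22) = 8.5 points. An exact 90% lower limit above 20% then needs 9/22 (41%, limit 23.3%), because 8/22 gives 19.6%.

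**The case against.** Much of the case on the other side stands.

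- **The larger figures need a rule that the looks cannot apply.** The endpoint falls 24 weeks after treatment ends, which is Week 72 in the 48-week schedule. Weeks 12 and 24 are on treatment or, in Cohort 9, at its end. A 3/8 rule on the endpoint is an upper illustration, and 3/8 appears in 6.1 only as a precision example.
- **Selection may be weak or absent.** Expansion may rest on safety, PK or other studies, and 6.11 does not itself link the looks to expansion.
- **Coverage is hurt less than it may seem.** A 90% limit allows 5% in the lower tail; 2.56% is low because the exact interval is conservative. At a true rate of 20%, the 2/8 rule (4.7%) and most of the marker cases stay within 5%. On the planned 95% interval, where 12/30 is needed, the chance given expansion is 1.8% (2/8 rule) or 3.5% (3/8 rule) against a nominal 2.5%.
- **The summaries are descriptive** (section 6) and the study is called hypothesis-generating (6.11). That removes any issue of error control. It does not remove bias in an estimate, and a descriptive study is read for its estimates.

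A reader might infer that 11/30 is a success criterion that will be met too often. The documents do not support this: 11/30 illustrates precision and no decision hangs on it. A look that can only withhold expansion also cannot raise the overall chance of reaching 11/30, as the last column of the table shows. Only the probability given expansion rises.

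**Conclusion.** The point holds in a limited form. The plan allows outcome-dependent expansion and then reports a plain pooled proportion. If expansion follows favourable early qHBsAg results, that proportion is biased upward in expanded cohorts. At a true rate of 20% the bias is about +0.3 to +3 points under an imperfect on-treatment marker, which is less than half a standard error. It reaches +5.8 points if expansion required at least 3/8 on the endpoint. The true rate and every expansion rule used here are assumptions; the documents fix neither, so the actual size cannot be known from them.

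The figures also assume 30 patients per cohort. Section 4.3 can be read as 30 across Cohorts 9 and 10, in which case fewer patients would be added and the first 8 would weigh more. Both the looks and the response-rate sizing apply to Cohort 10, so the point bears most directly there.

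A reader might also infer that any claim of a rate above 20% must rest on the added patients alone. The documents plan no such claim. Discarding 8 of 30 patients is a debatable trade, and because 4.3 lets the Sponsor enrol selected subgroups, the added patients may differ in kind from the first 8. Showing both stages is enough.

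**What to change.** - **Section 6.6.3:** for any expanded cohort, report the response rate and exact interval for the initial 8 and for the added patients, beside the pooled figure. Label the pooled figure as conditional on expansion.
- **Section 6.11:** state that the Week 12 and 24 looks may inform expansion, and record the data used for each expansion decision. A reader can then judge whether selection was on qHBsAg, safety, PK or outside data.

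The cost is one extra table and a short record per decision, with no added patients or visits. The downside is that the interval for the added patients is wider than the pooled one.
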